#### WE CALL IT "PLUG AND KNOW"

- 1 ..... Simply attach the Interface to your computer via a Standard USB (Universal Serial Bus) cable
- 2 ..... Automatically install the software Suite from a CD-ROM
- 3 ..... Immediately gain deeper insights into your patients' condition to improve and accelerate your decision making and/or treatment at the Point of Care

Wide interoperability via USB 2.0

#### Features and Benefits

##### Excellent Image Quality

- Superb Detail and Contrast Resolution
- Wide Bandwidth Architecture
- ArdentView Image Filters
- Capable of Imaging from 5.0MHz - 21MHz (transducer dependent)
- High Frame Rate: up to 139fps

##### Research

- Human: RF Out Capabilities
- Small Animal:
  - RF Out Capabilities
  - 1KHz M-Mode PRF

#### Clinical Utility

##### Superficial Structures

- High Frequency Linear: 5mm - 30mm
- 12MHz Linear Array: 15mm - 45mm

#### Technical Specifications

##### Physical Characteristics

- Height: 10.75 in (273 mm)
- Width: 4.75 in (121 mm)
- Length: 19.00 in (483 mm)
- Weight: 22 lbs (10 kg)

##### Transducer Options

- 5.0 - 8.0 MHz Convex Endo
- 9.0 - 14.0 MHz Linear Array
- 14.0 - 21.0 MHz Linear Array

##### Imaging Modes

- B-Mode
- B-M Mode
- M Mode
- Zoom (Pan)

##### Measurement Tools

- Distance
- Circumference
- Area
- Volume
- Beats/Minute (m-mode)

##### Image Storage & Cine

- Dicom Compatible
- Stores Images and Cine as Raw Data
- Export Images as bmp or jpg
- Export Cine as AVI
- Back-up Database to internal or external Hard Drive, CD, DVD or Network

**Power: 100-240 VAC  
50-60 Hz input**

##### Minimum Computer Requirements

Windows XP OS: USB 2.0 Port, 256 MB RAM, 1 GB Available Hard Drive Space

Windows7/ Vista OS: USB 2.0 Port, 500 MB RAM, >1 GHz Duo-Core Processor\*, 1 GB Available Hard Drive Space

\*assumes Windows7/ Vista Home OS.  
More Advanced Versions of Vista may require a faster processor and more RAM

## Appendix 6: Coupling Gel

[figure not shown]
# The best cosmetic quality lotion for medical ultrasound

## Polysonic® Ultrasound Lotion

**W**hen tough injuries call for gentle treatment, POLYSONIC® Ultrasound Lotion combines the pleasing appeal of a fine cosmetic with superior soundwave transmission. It transmits ultrasonic waves more efficiently than most gels, and is acoustically correct for medical ultrasound procedures.

The rich, moisturizing formulation of POLYSONIC® Ultrasound Lotion is the ideal medium for therapeutic ultrasound when followed with massage. It's kind to your skin as well as to your patients... and won't damage your equipment.

Our multi-purpose lotion, **also available with aloe vera**, is recommended for all medical ultrasound procedures... Another world-class quality product from Parker, a company dedicated to quality.

ISO 13485:2003

Parker Laboratories, Inc.

The sound choice in patient care.™

[contact]

www.parkerlabs.com

## POLYSONIC® ULTRASOUND LOTION

Multi-purpose ultrasound lotion with superior coupling efficiency in a pleasing, cosmetic-quality base. Recommended for all ultrasound procedures when a lotion is preferred. Also available, Polysonic Ultrasound Lotion with Aloe Vera.

### FEATURES

- Rich, moisturizing formula
- Comfortable and pleasing to patient and ultrasound practitioner
- Acoustically correct for the broad range of frequencies used
- Will not damage equipment or stain clothing
- Hypoallergenic, bacteriostatic
- No formaldehyde

Product #	Package Size
21-08	250 ml (8.5 fl. oz.) dispenser, 12 per box
21-28	3.8 liter (1 US gallon) with dispenser, 4 per case (Dispenser pump not included)
21-50	POLYPAC® contains: 4 Polysonic gallons, 2 dispensers and 1 pump
20-08 with Aloe Vera	250 ml (8.5 fl. oz.) dispenser, 12 per box
20-28 with Aloe Vera	3.8 liter (1 U.S. gallon) with dispenser, 4 per case (Dispenser pump not included)
20-50 with Aloe Vera	POLYPAC® contains: 4 Polysonic with Aloe Vera gallons, 2 refillable dispensers and 1 pump

ISO 13485:2003

Parker Laboratories, Inc.

The sound choice in patient care.™

[contact]

www.parkerlabs.com

TITLE: Preliminary Protocol for Intense Therapeutic Ultrasound for the Treatment of Chronic Plantar Fasciitis

PROTOCOL NO.: WIRB® Protocol #20160753

DATE: May 26, 2016

SPONSOR: Guided Therapy Systems

[name]

[name]

INVESTIGATOR: [name]

[name]

[name]

Statistical Approach:

- Pain Reduction:

Pain level at the plantar fascia was self-reported by subjects at pre-treatment (used as baseline measurement) and again at each follow-up - 4, 8, 12, and 26 weeks - after initial treatment. The pain scale subjects used to identify their level of pain was a 10-point pain scale range, where 0 = no pain, 1 = slight pain through 10 which equates to the patient's worst imaginable pain. The goal for all subjects in the treatment group was to reduce pain by at least 25%. For patients reporting an initial (baseline) score ranging 6-10, this reflects a VAS pain score reduction  $\geq$  a 2 point drop; for initial scores ranging 2-5, this reflects a VAS pain score reduction  $\geq$  a 1 point drop. Pain scores reported at follow-up timepoints were compared to baseline score for each subject to determine if the goal was met by dividing the difference in the follow-up and baseline pain score by the baseline pain score. The percentage of subjects that met the pain reduction goal was calculated at each timepoint for both control and treatment groups by dividing the number of subjects that achieved the pain reduction goal at each timepoint by the total number of patients that gave a pain score for that time point.

- Plantar Fascia Hypoechoic Lesion Size:

A large proportion of patients suffering from chronic plantar fasciitis present with hypoechoic lesions in or around the proximal plantar fascia, as viewed by diagnostic ultrasound imaging.

Hypoechoic lesions were imaged and volumes were calculated at the baseline visit and each follow-up visit by measuring the inferior-to-superior and posterior-to-anterior radii in the long axis and the medial-to-lateral radius of the transverse axis and applying the following formula for the volume of an ellipse:

$$\text{Volume} = (4/3)\pi \cdot r_1 \cdot r_2 \cdot r_3$$

With  $r_1$ ,  $r_2$ , and  $r_3$  representing the three radii detailed above. Changes to lesion volumes were recorded at each follow-up timepoint and compared to baseline by dividing the volume of the lesion at that timepoint with the volume of the same lesion at pre-treatment baseline.

- Foot Function Index Score Reduction:

In addition to the 10-point VAS pain scale, patients self-reported answers to questions from the Foot Function Index (FFI) pain subscale questionnaire, which has been standardized in a number of PF-focused publications . Scores range from 0-90, with 0 indicating no pain and 90 indicating the worst pain imaginable in a variety of daily activities involving use of the plantar fascia. Self-reported scores were taken at baseline and each follow-up timepoint. The average score for each timepoint were calculated, and follow-up averages were compared to baseline to calculate the percentage reduction in score.

- Hypoechoic Lesion Size – Pain/Function Correlation:

To determine the strength of a linear relationship between pain/function score reduction and lesion size reduction, linear regression was performed. Patient data related to pain/function score reduction at each follow-up timepoint compared to baseline were matched with corresponding data related to lesion size reduction. The average pain reduction percentage for each follow-up timepoint was paired with the average lesion size reduction percentage for the same follow-up timepoint to generate a data point for linear regression and the Pearson-correlation coefficient ( $r$ ) calculation.  $R$ -values found between 0.6 and 0.8 were considered strong and  $>0.8$  were considered very strong.

- Statistical Calculations

Student T-tests were utilized to determine statistically significant differences between baseline and subsequent follow-up measurements for self-reported and lesion size measurements. All error bars displayed in graphs are standard error. The level of significance ( $\alpha$ ) was set to 0.05.

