### ***Selection of Subjects***

The study population will consist of up to 30 subjects recruited from the associated UCLA outpatient clinics. The selection of suitable subjects will be made according to the inclusion and exclusion criteria described below.

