#### Statistical analysis

Data will be assessed for variance homogeneity and normality. FFI-P scores, PFCAT, FAAM scores before and after intervention will be compared using a paired t-test. Perifascial lesion volume is measured before and at each post treatment clinical visit using diagnostic ultrasound imaging, and paired t-tests will be utilized for comparison. For determination of statistical significance, a cutoff value of  $\alpha=0.05$  has been selected prior to start of data analysis.

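### On whole-point scores, the SAP's point-drop cut-offs do not match its own 25% pain-reduction goal at baselines 5, 9 and 10, so one set of scores can give two responder rates

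*SAP*

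**What the plan says.** The Pain Reduction paragraph of the SAP contains three statements about success on the 0-10 pain scale.

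- **Goal.** "The goal for all subjects in the treatment group was to reduce pain by at least 25" per cent.
- **Translation into points.** "For patients reporting an initial (baseline) score ranging 6-10, this reflects a VAS pain score reduction" of 2 points or more; "for initial scores ranging 2-5, this reflects a VAS pain score reduction" of 1 point or more.
- **Classification.** Each follow-up score is compared with baseline "to determine if the goal was met by dividing the difference in the follow-up and baseline pain score by the baseline pain score".

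A success rate is then reported at each timepoint for the control and treatment groups, dividing the number of successes "by the total number of patients that gave a pain score for that time point". The SAP gives no rounding rule and no order of precedence between the point statement and the division. The protocol does not define this responder goal, so it cannot settle the matter.

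**The concern.** The point statement is offered as equivalent to the 25% goal, and at some baselines it is not. Where the two differ, two analysts following the same paragraph could classify the same subject differently and report different success rates from identical data. A reader would also be told that a fall from 10 to 8 is a 25% reduction, when it is 20%.

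This is the first outcome the SAP describes and the only one with a numeric success target. The stakes are still bounded. The protocol's Statistical analysis section ("FFI-P scores, PFCAT, FAAM scores before and after intervention will be compared using a paired t-test") and the SAP's Statistical Calculations ("Student T-tests were utilized to determine statistically significant differences between baseline and subsequent follow-up measurements") specify t-tests on scores and lesion size. Neither specifies a test of the responder percentage, so the exposure is a descriptive result.

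**Working it through.** **Inputs.** From the SAP: goal of at least 25%; cut-offs of 1 point (baseline 2-5) and 2 points (baseline 6-10); success judged by change divided by baseline. From the protocol (Selection of Subjects): "The study population will consist of up to 30 subjects recruited from the associated UCLA outpatient clinics". Assumption: scores are whole numbers, as the SAP's anchors and bands suggest.

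**Step 1: do the stated cut-offs reproduce 25%?** The reduction at the cut-off is cut-off/baseline. The smallest whole-point drop that reaches 25% is 0.25 x baseline, rounded up.

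| Baseline | 25% of baseline | Smallest drop reaching 25% | SAP cut-off | Reduction at SAP cut-off | Agree? |
|---|---|---|---|---|---|
| 2 | 0.50 | 1 | 1 | 50.0% | yes |
| 3 | 0.75 | 1 | 1 | 33.3% | yes |
| 4 | 1.00 | 1 | 1 | 25.0% | yes |
| 5 | 1.25 | 2 | 1 | 20.0% | **no** |
| 6 | 1.50 | 2 | 2 | 33.3% | yes |
| 7 | 1.75 | 2 | 2 | 28.6% | yes |
| 8 | 2.00 | 2 | 2 | 25.0% | yes |
| 9 | 2.25 | 3 | 2 | 22.2% | **no** |
| 10 | 2.50 | 3 | 2 | 20.0% | **no** |

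**Step 2: which subjects are affected?** For baselines 2-10 there are 2 + 3 + ... + 10 = 54 possible improving changes. Classifying every baseline and follow-up pair under both rules, they disagree at exactly three: 5 to 4, 9 to 7 and 10 to 8. In each case the point rule calls success and the percentage rule does not.

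**Step 3: could rounding explain the cut-offs?** No. Rounding 0.25 x baseline to the nearest whole number with halves up gives 3 at baseline 10. With halves down, or halves to even, it gives 0 at baseline 2. The cut-offs fit any goal above 16.7% and up to 20%, so they match a 20% goal and not a 25% one.

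**Step 4: uncovered baselines.** Baseline 1 has no point rule, although 1 to 0 is a 100% reduction. At baseline 0 the ratio is undefined. That is unlikely, since entry requires heel pain, but its handling is not stated.

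**Step 5: size.** One reclassified subject moves the rate by 1/30 = 3.3 percentage points if 30 give a score, or 1/15 = 6.7 if 15 do (15 is an assumed group size). For illustration, take the change as normal, add it to baseline, round, and limit the result to 0-10. Use baselines uniform on 2-10, 4-10, 4-8 or 6-10; mean change 0, -1, -2, -3 or -4; and SD of change 1.5, 2, 2.5 or 3. That makes 4 x 5 x 4 = 80 scenarios. The point rule minus the percentage rule is:

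- smallest: 0.8 percentage points (baseline 4-8, mean -4, SD 1.5: 96.7% against 96.0%, difference taken before rounding);
- median: 4.7;
- largest: 10.5 (baseline 4-10, mean -2, SD 1.5: 69.1% against 58.6%).

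**The case against.** The best defence is that the SAP has one operative rule. The division sentence is the only one that says how attainment is determined, and the point statement is a gloss on the goal. On that reading the responder percentage is computed correctly and nothing is inflated. This is the more natural reading, and it stands as a limit on the consequence. It does not rescue the gloss, which is still wrong at three baselines, and the SAP nowhere says that it is only illustrative.

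Three further points have weight.

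- **Direction.** The one-way direction depends on whole-point scores. The SAP calls the measure a VAS and does not state that scores are whole numbers. With half-points, a fall from 6 to 4.5 or from 2 to 1.5 reaches 25% but misses the point cut-off, so the disagreement can run the other way.
- **Illustrative range.** It rests on inputs that the documents do not supply. Every assumed baseline distribution includes 5, or 9 and 10, so the non-zero minimum is built in. Baselines confined to 2-4 and 6-8 would give no difference. Even with the point rule, there is no overstatement if nobody makes one of the three changes.
- **Baselines 0 and 1.** These are secondary. The division already handles 1 to 0, and excluding baseline 0 changes the stated denominator, so it is a choice to be declared.

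**Conclusion.** The concern holds and should be fixed. On whole-point scores, the stated cut-offs contradict the 25% goal at three of nine baselines. The real effect on the rate is zero if the division was used. If the point rule was used, the error within baselines 2-10 is 3.3 percentage points per affected subject with 30 scored, always upwards. The 0.8 to 10.5 range shows what is possible under the stated assumptions and does not estimate what occurred, since the documents give no baseline distribution. The planned t-tests are untouched.

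**What to change.** 1. Define success once: (baseline - follow-up)/baseline >= 0.25.
2. Delete the point statement or, if whole-point equivalents are wanted, correct it to at least 1 point for baseline 1-4, at least 2 for 5-8 and at least 3 for 9-10. With these, the two forms agree for every whole-point pair with baseline 1-10.
3. State whether scores are whole numbers, and state that a subject with baseline 0 is outside both numerator and denominator.
4. Confirm that the reported rates use this rule, and give the number of subjects at each timepoint whose change was 5 to 4, 9 to 7 or 10 to 8.

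The cost is about one sentence of the SAP and a recount of existing scores, with no new data. The downside is that the reported success rate may come out slightly lower if the point cut-offs had been used.

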More than twenty different treatments have been used for plantar fasciitis [14]. The combination of rest, ice, stretching and NSAIDs are used as initial management in most patients and have been shown to effectively treat symptoms in 90% of patients in less than 12 months [6]. However, 10% of patients fail conservative management and continue to have symptoms beyond 12 months (termed refractory plantar fasciitis or RPF) [1, 15, 16]. Surgery consisting of partial plantar fascia release or gastrocnemius recession is often considered in these patients. However, the outcomes of surgery are not uniformly positive with 50% of patients having residual symptoms. Moreover, evidence supporting surgical treatment of RPF is weak as there are no randomized controlled trials comparing its efficacy to other treatments. Thus, for many patients the risks of surgery such as arch instability, prolonged wound healing, and longer rehabilitation times simply outweigh the benefits [1]. ITU may be a non-invasive treatment that can be used as an adjunct to speed healing in patients with CPF and as an alternative to surgery in those with RPF.

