### ***Purpose of Study***

The purpose of this study is to assess the effectiveness of ITU in the treatment of CPF by assessing pain, function, and change in perifascial lesions treated with ITU in addition to standard of care. The primary outcome measures will be clinical grading for plantar fasciitis/osis grading and subject reported questionnaires where pain, function and level of activity will be compared before, during and at 24 weeks after the first of 2 treatments. In addition diagnostic ultrasound images will assess the change of any perifascial hypoechoic lesions. Finally, the safety and tolerability of ITU will be monitored through the course of the study. It is hypothesized that patients receiving ITU in addition to standard of care will have a more rapid resolution of their pain, faster return to activities, and a decrease in perifascial lesions.

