### ***Materials and Methods***

The **primary objective** of this study is to evaluate the efficacy of combining intense therapeutic ultrasound (ITU) with standard care, including post-treatment therapy, exercises and boot immobilization for the treatment

of chronic plantar fasciitis/osis. A **secondary objective is to** evaluate the tolerability and safety of intense therapeutic ultrasound in the treatment of plantar fasciitis.

These objectives will be accomplished through the following specific aims:

**Aim # 1:** Compare subject reported outcomes of pain, function and level of activity for all subjects before and after treatment. Follow the subjects for 24 weeks by clinic visits and phone surveys.

**Aim # 2:** Compare the changes in perifascial lesion volume for all subjects before and after treatment by diagnostic ultrasound imaging. Follow the subjects for 12 weeks by clinic visits.

**Aim # 3:** Evaluate the tolerability and safety of ITU for the treatment of the chronic plantar fasciitis.

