#### ***Inclusion Criteria***

Male and female adults (18 to 70 years) with plantar heel pain and point tenderness near the medial calcaneal insertion of the plantar fascia for at least three months without improvement will be considered for inclusion into the study.

Subjects must be willing and able to follow post treatment regimen including immobilization boot for 2 - 4 weeks after each treatment, and massage therapy.

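### The SAP reports pain-responder rates for a control group that the available text never defines, and the comparative speed hypothesis has no between-group contrast or interval

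*SAP*

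**What the plan says.** **SAP, Pain Reduction.** The responder goal is set for one group: "The goal for all subjects in the treatment group was to reduce pain by at least 25" per cent. The percentage meeting it "was calculated at each timepoint for both control and treatment groups", with the subjects who gave a score at that timepoint as denominator.

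**Protocol, Purpose of Study.** The hypothesis is comparative: "It is hypothesized that patients receiving ITU in addition to standard of care will have a more rapid resolution of their pain". It continues with a faster return to activities and a decrease in lesions.

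**Protocol, Materials and Methods.** The primary objective is to "evaluate the efficacy of combining intense therapeutic ultrasound (ITU) with standard care". Aim 1 is to "Compare subject reported outcomes of pain, function and level of activity for all subjects before and after treatment", and Aim 2 has the same before/after form for lesion volume.

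**Protocol, Selection of Subjects.** "The study population will consist of up to 30 subjects recruited from the associated UCLA outpatient clinics". No split by group is given.

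**Protocol, Interventions and Timeline.** There is a single schedule. ITU at Visit 1 is unconditional; only the second treatment is conditional. Boot, insert and massage accompany ITU.

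**Tests.** The protocol's Statistical analysis section names paired t-tests before and after intervention. The SAP's Statistical Calculations section names Student t-tests of baseline against follow-up, with standard-error bars on graphs and α = 0.05.

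**The concern.** Two things do not fit together. First, the SAP promises a result for a group whose source, number, allocation and treatment appear nowhere in the available text. Second, a claim that recovery is quicker with ITU added to standard care needs something to be quicker than, and no named analysis makes that comparison.

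The protocol itself gives reason to expect improvement without ITU. Its Background says that first-line conservative care (NSAIDs, stretching, ice and rest) "have been shown to effectively treat symptoms in 90% of patients in less than 12 months". Subjects with heel pain "for at least three months without improvement will be considered for inclusion into the study", so some enter within the period over which that recovery is described. Choosing people because their symptoms persist also invites regression to the mean.

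At stake is the conclusion. A significant paired t-test or a high responder percentage could be read as showing that ITU works, when the plan as written would produce the same result from the accompanying care or from time alone.

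**Working it through.** The plan states no power, SD, effect size or control rate, so there is no figure of its own to reproduce. The main check is textual; the arithmetic only illustrates it.

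**Step 1: look for a control group.**
- Selection of Subjects: one population, up to 30.
- Aims 1 and 2: all subjects, before against after.
- Interventions: a second treatment at week 4 depends on the response so far, which presumes that everyone had a first.
- Timeline: one column sequence, with ITU at Visit 1 for all.
- Aim 2 imaging: the other foot is imaged, but bilateral heel pain is an exclusion and that foot is given no pain score. It cannot supply a pain-responder rate.

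No section describes a sham, a standard-care-only arm, a historical comparator or an allocation.

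**Step 2: look for a between-group analysis.** The protocol's paired t-tests and the SAP's Student t-tests are both within-group. The responder percentages carry no test or interval. The regression relates average pain reduction to average lesion reduction and does not compare groups. There is no time-to-response analysis.

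**Step 3: what the planned test shows if ITU adds nothing.** Assume a common improvement of d SDs of the change score from other causes, two-sided α = 0.05 (sidedness is not stated), and n = 30, the protocol's maximum. Then

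P(significant) = 1 − F(t₀.₉₇₅; n − 1 df, noncentrality d√n),

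where F is the noncentral t distribution; the opposite tail is negligible. At n = 30, t₀.₉₇₅ = 2.045. As the documents give no dropout figure, n = 20 is shown as a second assumption (t₀.₉₇₅ = 2.093).

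| assumed d | d√30 | P, n = 30 | d√20 | P, n = 20 |
|---|---|---|---|---|
| 0.3 | 1.64 | 0.36 | 1.34 | 0.25 |
| 0.5 | 2.74 | 0.75 | 2.24 | 0.56 |
| 0.8 | 4.38 | 0.99 | 3.58 | 0.92 |

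The test is doing its job here: it detects a real change. It says nothing about the cause.

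**Step 4: precision after correction.**
- No controls, n = 30: the 95% CI half-width for mean change is 2.045/√30 = 0.37 SD of the change. The exact 95% CI for 15 of 30 responders is 31% to 69%.
- Controls exist, 30 treated and m controls (m assumed), 50% responders in each group (assumed): half-width = 1.96 × √(0.25/30 + 0.25/m), which gives 0.358 for m = 10, 0.283 for m = 20 and 0.253 for m = 30.

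**The case against.** **Uncontrolled pilot studies are legitimate, and the aims are openly before/after.** This stands. The objective speaks of combining ITU with standard care, so the package is already partly acknowledged. The point is not that a control arm is required. It is that the control wording and the comparative hypothesis do not match the design described.

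**The responder calculation can be done.** This stands for treated subjects, where numerator, denominator and timepoints are all given. A reader might infer that the whole calculation fails; only the control half is undefined.

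**Controls may exist after all.** This is possible. Some pages, including those between Appendix 1-F and Appendix 3, are not in the available text. The word may also have come from elsewhere:
- The SAP cites its reference 7 for lesions seen on ultrasound, but the protocol's reference 7 is an MR imaging paper.
- The SAP cites 8–10 for the Foot Function Index, but the protocol's 8–10 are ultrasound papers.
- The SAP has a 26-week follow-up where the protocol has 24 weeks.
- The SAP is in the past tense, and the protocol describes an earlier study of the same treatment with 28 completed subjects.

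This suggests text carried over from another report but does not prove it. The attribution problem is therefore conditional on there being no controls. The missing between-group analysis is not: if controls exist, the SAP gives them descriptive percentages only.

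**Requiring three months without improvement removes natural recovery.** It selects slower recoverers, but does not rule out later recovery or regression to the mean.

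**Conclusion.** The concern holds in this form. The SAP refers to a control group that the available text does not define, and no planned analysis tests the comparative hypothesis in Purpose of Study. If there are no controls, change from baseline cannot be attributed to ITU alone. This should be corrected before results are interpreted, because following the plan would let a within-group change stand as evidence for a comparative claim.

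The conclusion is qualitative and rests on the text. The 75% and 99% figures depend on assumed improvements of 0.5 and 0.8 SD at n = 30 and show only that the test cannot separate causes.

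Two stronger readings are not supported. A reader might turn the Background's 90% recovery within 12 months into an expected responder rate without ITU. That figure describes successful treatment of symptoms under different care, whereas the SAP counts a 25% drop in pain, and the inclusion criterion selects people who have not improved. The documents do not allow the conversion. Nor do they show that ITU is ineffective; they show that this plan cannot tell.

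**What to change.** **1. Settle the fact.** State in the SAP whether this study has a control group, or whether the word refers to other data or was carried over from another report.

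**2a. If there is no control group:**
- In the SAP's Pain Reduction section, make the percentages apply 'for all treated subjects' and the goal to 'all subjects'.
- Add a 95% CI for mean change beside each paired t-test (protocol Statistical analysis; SAP Statistical Calculations) and an exact 95% CI for each responder percentage.
- State that the comparative hypothesis in Purpose of Study is not tested and that change from baseline will not be attributed to ITU alone.
- If data have not been analysed, also remove *more rapid* and *faster* from that hypothesis. If they have, leave the hypothesis as written and record the change in a dated post hoc SAP note.

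**2b. If controls exist:**
- Describe their source, number, allocation, treatment and the measures collected.
- Report the between-group difference in pain responders with a 95% CI at each timepoint collected.
- Add a longitudinal or time-to-response contrast for the speed claim; a responder difference at one visit does not measure speed.
- Label these analyses post hoc if data have been seen, and confounded if controls were not randomised.

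**Cost.** 2a needs wording and intervals, with no new data. 2b needs a description and added analyses of whatever was collected. Its intervals would be wide: about 25 to 36 percentage points either side with 30 treated and an assumed 30 down to 10 controls at 50% responders. Either way the downside is a more modest claim. Treatment and visit schedules are untouched.
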